## 5.1. DATA MONITORING COMMITTEE (DMC)

There will be no statistical analyses for DMC for this study.

## 5.2. INTERIM ANALYSIS

There will be no Interim Analysis for this study.

## 5.3. FINAL ANALYSIS

All final, planned analyses identified in this SAP will be performed by SPARC Consulting, Milan, Italy on behalf of IQVIA RDS Italy, Milan, Italy following Sponsor Authorization of this Statistical Analysis Plan, Database Lock, Sponsor Authorization of Analysis Sets and Unblinding of Study Treatment.

The default summary statistics for quantitative variables will be the number of observations (n), mean, standard deviation (SD), median, minimum (min) and maximum (max) for those patients with data. For quantitative efficacy variables, standard error of the mean (SEM) and lower and upper 95% confidence limits (CI) for mean will be also presented.

For qualitative variables, the number (n) and percentage (%) of patients with non-missing data per category will be the default summary presentation, and where appropriate and present, the number of missing values as a "Missing" category. If appropriate, 95% confidence intervals around the proportions will be presented using the Clopper-Pearson's formula.

## 6. ANALYSIS SETS

Agreement and authorization of patients included/excluded from each analysis set will be performed on a case-by-case basis before the database lock. A blind data review meeting will be held before database lock and before opening randomization codes, in order to assign the patients to each of the analysis sets according to the specified definitions. Patient's exclusion from each of the analysis sets will be documented and justified in a Blind Data Review Report.

### 6.1. ALL SUBJECTS ENROLLED SET [ENR]

The enrolled (ENR) set will contain all patients who provided informed consent for this study.

### 6.2. RANDOMIZED ANALYSIS SET [RND]

The Randomized Analysis (RND) set will contain all patients in the ENR set who were randomized to the study, regardless of whether they received study medication or not.

---

Document: MEX0114\_SAP\_v4\_4 Final Methods.docx  
Author: [name]

Version Number: Final Version 4.4  
Version Date: [17SEP2019]

Template No: CS\_TP\_BS016 – Revision 4  
Effective Date: 01Apr2016

Reference: CS\_WI\_BS005

### 6.3. SAFETY ANALYSIS SET [SAF]

The Safety Analysis (SAF) set will contain all patients in the RND set who received any study medication and will be based on the treatment actually received.

### 6.4. INTENT TO TREAT SET [ITT]

The Intent to Treat (ITT) set will contain all patients who were randomized and received at least one dose of study medication (either Ladarixin or placebo). It will be based on the treatment randomized, regardless of the treatment actually received. The ITT set will be used to present efficacy data.

### 6.5. PROTOCOL DEVIATIONS

All the protocol deviations will be discussed case by case by the clinical team during the review of the data before the lock of the study database and described in the Blind Data Review Report.

However, the following protocol deviations are anticipated to be considered as major:

- Inclusion and exclusion criteria not respected;
- Received treatment other than they were randomized to;
- Missing information on IMP administration that does not allow calculation of IMP exposure/compliance;
- Overall study treatment compliance < 80%;
- Incorrect Boost dose at one or more MMTT visits;
- Missing data for the primary endpoint (AUC C-peptide from MMTT at week 13);
- Primary endpoint (AUC C-peptide from MMTT) at week 13 assessed out-of-window visit ( $\pm 1$  week);
- Use of prohibited concomitant medications prior to enrolment and up to the end of the study participation (Concomitant treatment with phenytoin, warfarin, sulphonylurea hypoglycemics (e.g. tolbutamide, glipizide, glibenclamide/glyburide, glimepiride, nateglinide) and high dose of amitriptyline (> 50 mg/day), concomitant treatment with metformin, sulfonylureas, glinides, thiazolidinediones, exenatide, liraglutide, DPP-IV inhibitors or amylin, or any medications known to influence glucose tolerance (e.g.  $\beta$ -blockers, angiotensin-converting enzyme inhibitors, interferons, quinidine antimalarial drugs, lithium, niacin, etc.), current administration of any immunosuppressive medications (including oral, inhaled or systemically injected steroids) and use of any investigational agents, including any agents that impact the immune response or the cytokine system);
- Concurrent illnesses/TEAEs that may impact the glycemic control or trial read-out, to be defined case by case.

## 7. GENERAL CONSIDERATIONS

### 7.1. REFERENCE START DATE AND STUDY DAY

Randomization is defined as Study Day 0 with reference to day when IMP administration is started, which is defined as Study Day 1.

In general, reference start date is defined as the day of the first dose of study medication (Study Day 1: first day in

---

Document: MEX0114\_SAP\_v4\_4 Final Methods.docx  
Author: [name]

Version Number:  
Version Date:

Final Version 4.4  
[17SEP2019]

Template No: CS\_TP\_BS016 – Revision 4  
Effective Date: 01Apr2016

Reference: CS\_WI\_BS005

Week 1), and will appear in every listing where an assessment date or event date appears. However, different reference start date could be used in the statistical analysis according to the objective of the analysis. In such case, notes defining the reference start date will be added in the statistical tables and line listings.

Study Day will be calculated from the reference start date, and will be used to show start / stop day of assessments and events.

- If the date of the event is on or after the reference start date then:

Study Day = (date of event – reference start date) + 1

- If the date of the event is prior to the reference start date then:

Study Day = (date of event – reference start date)

In the situation where the event date is partial or missing, the date will appear partial or missing in the listings, and Study Day and any corresponding duration will be presented based on the imputations specified in Appendix 2 (Partial Date Conventions).

## 7.2. STUDY BASELINE

Unless otherwise specified, study baseline is defined as the last non-missing measurement taken prior to IMP administration (including unscheduled assessments). In the analysis of MMTT variables (Glucose, C-peptide and Glucagon) (reported and calculated parameters) the Basal of those variables is defined as the average of the two basal values (Basal #1 and Basal #2 (pre-meal values)). If one of the two basal values is missing the non-missing basal value will be considered as Basal in the analysis of MMTT variables.

## 7.3. RETESTS, UNSCHEDULED VISITS AND EARLY TERMINATION DATA

No unscheduled visits have been foreseen in the study.

In general, for by-visit summaries, data recorded at the nominal visit will be presented. Unscheduled measurements will not be included in by-visit summaries.

Listings will include scheduled, unscheduled and early discontinuation data.

## 7.4. WINDOWING CONVENTIONS

Actual dates of visits will be used for calculations of time intervals. No visit windowing will be performed for this study. Out-of-window visits will not be reallocated to the nearest timepoint.

## 7.5. STATISTICAL TESTS

All statistical tests will be performed one sided with  $\alpha=0.05$  and 95% confidence intervals will be employed, unless otherwise specified in the description of the analyses.

## 7.6. COMMON CALCULATIONS

For some quantitative measurements, change from baseline will be calculated as:

- Absolute: Value at Visit X – Baseline Value

---

Document: MEX0114\_SAP\_v4\_4 Final Methods.docx  
Author: [name]

Version Number:  
Version Date:

Final Version 4.4  
[17SEP2019]

Template No: CS\_TP\_BS016 – Revision 4  
Effective Date: 01Apr2016

Reference: CS\_WI\_BS005

- Relative:  $((\text{Value at Visit X} - \text{Baseline Value}) / \text{Baseline Value}) * 100$

## 7.7. SOFTWARE VERSION

All statistical analyses will be conducted using The SAS System version 9.4 under Windows 10 PRO operating system.

## 8. STATISTICAL CONSIDERATIONS

### 8.1. ADJUSTMENTS FOR COVARIATES AND FACTORS TO BE INCLUDED IN ANALYSES

In the analysis of secondary efficacy variables 2-hour AUC of C-peptide response to the MMTT, average (previous 3 days) insulin requirement (IU/kg/day), HbA1c levels, and C-peptide AUC (15-120) above fasting value the following fixed factors will be considered in the mixed linear model:

- Treatment group
- Visit
- Treatment by visit interaction

In the analysis of percent change from baseline in 2-hour AUC of C-peptide response to the MMTT the baseline value of 2-hour AUC of C-peptide will be considered as a covariate of the mixed linear model. Moreover, treatment group, visit and the treatment by visit interaction will be the fixed effects of the mixed linear model.

In the analysis of actual values of the efficacy endpoints C-peptide, Glucose and Glucagon over the study the following fixed factors will be considered in the mixed linear model:

- Treatment group
- Visit
- Time
- Treatment by visit interaction
- Treatment by time interaction
- Treatment by visit and by time interaction

In the analysis of 2-hour AUC C-peptide according to the number of positivity in auto-antibodies counted at Screening visit the following fixed factors will be considered in the mixed linear model:

- Treatment group
- Visit
- Treatment by visit interaction
- Number of positivity
- Treatment by number of positivity interaction

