- Baseline MMTT. Blood samples for measurement (centralized laboratory) of C-peptide, glucose and glucagon will be drawn pre-meal (2 basal samples in the range between -20 to 0 min) and 15, 30, 60, 90, 120, 180 min after the meal. Procedures for MMTT and sample handling are detailed in [Appendix 14.4.2](#) and [Appendix 14.4.1](#), respectively. MMTT should not be performed within one week of resolution of a diabetic ketoacidosis event;

For the purpose of this protocol, a diabetic ketoacidosis event is defined as the presence of:

hyperglycemia (blood glucose >200 mg/dL);
pH <7.3 or HCO₃ <15;
ketones positive in the serum or urine.

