## 16.2. SECONDARY EFFICACY ANALYSES

### 16.2.1. SECONDARY EFFICACY VARIABLES

The secondary efficacy variables are:

1. 2-hour AUC of C-peptide response to the MMTT [Time points: baseline, weeks 13±1, 26±2 and 52±2].
2. Percent change from baseline of 2-hour AUC of C-peptide response to the MMTT [Time points: weeks 13±1, 26±2 and 52±2].
3. Average (previous 3 days) insulin requirement (IU/kg/day) [Time points: baseline, weeks 13±1, 26±2 and 52±2].  
For the patients reporting “off insulin” response in the CRF the daily insulin requirement value will be conventionally set to zero in the statistical analysis.
4. HbA1c levels [Time points: baseline, weeks 13±1, 26±2 and 52±2].
5. Number of severe hypoglycemic events occurring from randomization [Time points: weeks 13±1, 26±2 and 52±2].  
A severe hypoglycemic event is defined as an event with one of the following symptoms: “Memory loss, confusion, uncontrollable behavior, irrational behavior, unusual difficulty in awakening, suspected seizure, seizure, loss of consciousness, or visual symptoms”, in which the patient was unable to treat him/herself and which was associated with either a blood glucose level < 54 mg/dL or prompt recovery after oral carbohydrate, i.v. glucose, or glucagon administration.
6. Basal (2 basal samples in the range between -20 to 0 min) to 180 min time course of C-peptide and glucose derived from the MMTT [Time points: baseline, weeks 13±1, 26±2 and 52±2].
7. Proportion of patients maintaining a residual β-cell function [Time points: baseline, weeks 13±1, 26±2 and 52±2].  
Maintenance of a residual β-cell function is defined as at least one MMTT C-peptide value > 0.2 nmol/L.
8. Proportion of patients with HbA1c < 7% and absence of episodes of severe hypoglycemia from the previous visit [Time points: weeks 13±1, 26±2 and 52±2].
9. C-peptide AUC (15-120 minutes) above fasting value [Time points: baseline, weeks 13±1, 26±2 and 52±2].

Document: MEX0114\_SAP\_v4\_4 Final Methods.docx  
 Author: [name]

Version Number:  
 Version Date:

Final Version 4.4  
 [17SEP2019]

Template No: CS\_TP\_BS016 – Revision 4  
 Effective Date: 01Apr2016

Reference: CS\_WI\_BS005

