6. The comparisons between groups on the C-peptide and glucose in terms of basal to 180 min time course will be carried-out using a mixed linear model with C-peptide and glucose derived from the MMTT as dependent variables, treatment group, visit, time, treatment by visit interaction, time by visit interaction and treatment by time by visit interaction as fixed factors of the model and patient as random effect. An unstructured covariance matrix for each patient is considered and the Kenward-Roger adjustment is used for the degrees of freedom. Furthermore, default summary statistics of Cmax and Tmax of the MMTT at each visit will be provided. Cmax and Tmax will be calculated up to 180 minutes after mixed meal administration (time interval ranging from 15 min. to 180 min.). Individual plots will be presented. Based on the observed trends, additional analyses might be performed.
7. Number and proportion along the 95% confidence interval (Clopper-Pearson's formula) of patients maintaining a residual  $\beta$ -cell function at the single time points will be calculated. The comparison between the two study treatment arms will be performed by means of a Chi-square test or, if more appropriate, a Fisher's Exact test at each time point.
8. Number and proportion along the 95% confidence interval (Clopper-Pearson's formula) of patients with HbA1c < 7% and absence of episodes of severe hypoglycemia from the previous visit will be calculated for each time point. The comparison between the two study treatment arms will be performed by means of a Chi-square test or, if more appropriate, a Fisher's Exact test at each time point.
9. The comparisons between groups on C-peptide AUC (15-120) above fasting value will be carried-out using a mixed linear model where the  $\log(x+1)$  transformed C-peptide AUC above fasting value will be the dependent variable, while treatment group, visit, treatment by visit interaction will be the fixed factors of the model and patient will be the random effect. An unstructured covariance matrix for each patient is considered and the Kenward-Roger adjustment is used for the degrees of freedom.

---

Document: MEX0114\_SAP\_v4\_4 Final Methods.docx  
Author: [name]

Version Number:  
Version Date:

Final Version 4.4  
[17SEP2019]

Template No: CS\_TP\_BS016 – Revision 4  
Effective Date: 01Apr2016

Reference: CS\_WI\_BS005

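### SAP 8.1 and SAP 16.2.2/16.3.2 list different fixed effects for the meal-test time-course model and neither list is complete; under 8.1 the three-way test can reject with no treatment effect

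*SAP*

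**What the plan says.** SAP 8.1 gives one list for the analysis of C-peptide, glucose and glucagon values over the study: treatment, visit, time, treatment by visit, "Treatment by time interaction", and "Treatment by visit and by time interaction". Visit by time is absent.

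SAP 16.2.2 item 6, for C-peptide and glucose, lists "treatment group, visit, time, treatment by visit interaction, time by visit interaction and treatment by time by visit interaction as fixed factors". Here visit by time is present and treatment by time is absent. SAP 16.3.2 repeats that second list for glucagon (exploratory endpoint 1).

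SAP 4.3, which records changes from the protocol, does not mention the difference. Protocol 9.4.2 cannot settle it, because it names no model for the time courses. SAP 8.4 makes only the primary comparison confirmatory, so these analyses are secondary (C-peptide, glucose) or exploratory (glucagon).

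**The concern.** Two lists for one model leave the programmer to choose, and the choice changes what the interaction tests mean. When a two-way term is left out of a model that keeps the three-way term, its degrees of freedom move into the three-way term.

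Under 8.1 the term that moves is visit by time, which contains no treatment contrast. A result labelled as a treatment interaction would then partly test whether the meal curve changes shape over the year in all patients. Such change is plausible: Protocol 9.1 refers to C-peptide decline over time in this disease.

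Under 16.2.2 and 16.3.2 the term that moves is treatment by time. The result is still about treatment, but it mixes two questions, and treatment by time has no test of its own.

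**Working it through.** **Inputs from the documents**
- Arms: 2.
- Visits: 4, from SAP 16.2.1: "time course of C-peptide and glucose derived from the MMTT [Time points: baseline, weeks 13±1, 26±2 and 52±2".
- Sampling times: 7. Six are post-meal (Protocol 7.1.2: "15, 30, 60, 90, 120, 180 min after the meal"). One is basal, because SAP 7.2 says the basal value "is defined as the average of the two basal values".
- Patients: 72 randomised 2:1, so 48:24. With the planned 24% drop-out, 72 × 0.76 = 54.7, taken as 55 (37:18).
- Level: 0.05. SAP 7.5 states "All statistical tests will be performed one sided with" that level, but an interaction F test has no side.

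The plan states no figure for these tests, so there is none to reproduce.

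**Degrees of freedom**

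The terms contribute: intercept 1, treatment 1, visit 3, time 6, treatment by visit 3, treatment by time 6, visit by time 18. There are 2 × 4 × 7 = 56 cells, and every list that keeps the three-way term spans all 56.

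| List | Rank without three-way term | df of three-way test | What the test contains |
|---|---|---|---|
| SAP 8.1 | 1+1+3+6+3+6 = 20 | 56 − 20 = 36 | 18 three-way + 18 visit by time |
| SAP 16.2.2 / 16.3.2 | 1+1+3+6+3+18 = 32 | 56 − 32 = 24 | 18 three-way + 6 treatment by time |
| All terms | 1+1+3+6+3+6+18 = 38 | 56 − 38 = 18 | three-way only |

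Numerical ranks of the design matrices confirm 20, 32 and 38.

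**Why a proportional decline matters**

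Suppose the basal value is 0.35 and the peak 0.85 nmol/L (assumed). A 30% fall lowers them by 0.30 × 0.35 = 0.105 and 0.30 × 0.85 = 0.255. The peak-to-basal rise shrinks from 0.50 to 0.35, which is a visit-by-time effect even if both arms behave identically.

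**Null rejection rates**

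Simulation with no treatment effect, complete data, a patient random intercept (SD 0.3), independent residuals and 1,000 runs per setting. The assumed curve is 0.35, 0.45, 0.60, 0.80, 0.85, 0.80, 0.60 nmol/L from basal to 180 min. Visit multipliers are 1, 0.95, 0.90, 0.80 (20% decline) or 1, 0.95, 0.85, 0.70 (30%). Each range runs over residual SD 0.20 down to 0.10 nmol/L.

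| Change common to both arms | 8.1 list, 72 patients | 8.1 list, 55 patients |
|---|---|---|
| None | 0.046-0.048 | 0.054-0.055 |
| 20% proportional decline | 0.27-0.93 | 0.18-0.80 |
| 30% proportional decline | 0.67-1.00 | 0.50-1.00 |

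In the same settings the 16.2.2/16.3.2 list gives 0.036-0.058 and the complete list 0.036-0.059. A parallel shift of the whole curve (72 patients, SD 0.15) gives 0.046 under 8.1.

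**Covariance as the SAP specifies it**

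The SAP asks for an unstructured matrix with Kenward-Roger degrees of freedom. A multivariate test of the same 8.1 hypothesis stands in for that (72 patients, complete data). It rejects in 0.19-0.80 of null trials for a 20% decline and 0.37-0.99 for a 30% decline over the same SD range. With fewer evaluable patients these rates would be lower, so the bottom of the range is approximate.

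**The case against.** The strongest reply is that the sections describing how the analysis is run, 16.2.2 and 16.3.2, both contain visit by time. The inflation arises only if the list in 8.1 is followed instead. That is right, and it makes this an ambiguity rather than a settled plan to run an invalid test. It does not remove the point, because no section gives either list precedence.

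Three stronger readings are tempting, and the documents do not support them.
- **Any change over visits shared by both arms inflates the test.** It does not. A uniform shift goes into the visit main effect. Only a change in curve shape matters, and whether shape changes depends on scale: a proportional decline is parallel after a log transform, and a check on that scale rejected in 0.04. SAP 8.1 refers to actual values, and the log transform in SAP 16 is stated for AUC, so the untransformed scale is the natural reading.
- **A single high rejection rate describes the plan.** For a 30% decline, SD 0.15 and 72 patients, the independent-error simulation gives 0.95 and the multivariate version 0.76. Curve, decline and SD are all assumed, so only a range is defensible.
- **The plan would produce a false efficacy signal.** The three-way F test has no direction and is not confirmatory, and no section names it as the result that carries the group comparison. The estimates that would show benefit, the treatment contrasts at each visit and time, are the same under every list because all the lists fit the same 56 cell means.

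Nor should 16.2.2 be taken as the correct list. It keeps the null rate near 5%, but its 24-df test is not a pure three-way test either.

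**Conclusion.** The lists conflict and neither is complete. This follows from the text and from counting degrees of freedom, and needs no assumption. Taken literally, 8.1 yields a three-way test in which 18 of the 36 degrees of freedom have nothing to do with treatment, so it is not valid as a treatment test when the untransformed curve changes shape in both arms.

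The size of the inflation does rest on assumptions. For common declines of 20-30% and residual SD 0.10-0.20 nmol/L it runs from about 0.2 to 1.0, against a nominal 0.05, depending on the covariance model and the number of evaluable patients. With no change over visits, or a parallel one, there is no inflation.

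The reach is narrow: interaction F tests on secondary and exploratory endpoints. This is a minor correction, but a clear one.

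**What to change.** Put one identical list in SAP 8.1, 16.2.2 item 6 and 16.3.2 (glucagon): treatment, visit, time, treatment by visit, treatment by time, visit by time, and treatment by visit by time. The three-way test then has 18 degrees of freedom, treatment by time gets its own test, and the simulated null rejection rate is 0.036-0.059 in every setting tried.

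The cost is one line in each of three sections. It needs no new data, leaves the fitted means unchanged and does not touch the primary analysis.

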### 8.2. MULTICENTRE STUDIES

This study will be conducted by multiple investigators at multiple centers. Site-related differences will not be evaluated and presented in the statistical output as the study does not foresee a randomization stratified by Centre.

---

Document: MEX0114\_SAP\_v4\_4 Final Methods.docx  
Author: [name]

Version Number: Final Version 4.4  
Version Date: [17SEP2019]

Template No: CS\_TP\_BS016 – Revision 4  
Effective Date: 01Apr2016

Reference: CS\_WI\_BS005

